## **2.6 Secondary Outcome Parameters**

The secondary outcome parameters will include:

- Changes in liver function between the 3 groups.
- Changes in estrogen levels (E2) between the 3 groups.
- Changes in endometrial thickness and ovarian characteristics between the 3 groups.
- Change in the pharmacokinetic parameters of EGCG and metabolites within each group.
- Difference in serum folate levels among wildtype MTHFR, MTHFR (C677T), and MTHFR (A1298C) patients.

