## **2.7 Statistical Analysis**

Since the number of patients for this study is minimal and multiple factors are of concern, descriptive statistics will be used, and the study is expected to be under powered to perform any formal statistical inference. The number, mean, standard deviation, median, interquartile range of the level of the pharmacokinetic parameters of EGCG and 2 of the major metabolites at different time points and the difference from screening to Visit 1, Visit 2 or Visit 4, and the changes in liver function, estrogen levels, endometrial thickness, and follicular measurements will be presented for the three treatment groups, and then stratified by age group and/or the presence or absence of uterine fibroid. For comparison, a two-way ANOVA will be used to compare the effects of the three treatments and the presence of fibroids on the above outcome parameters. With a sample size of 36 patients for the three treatment groups, which includes 18 subjects with uterine fibroids and 18 without uterine fibroids, with an alpha of 0.05, the power of the study would be 0.44 and 0.85 for a medium (0.25) or large (0.4) effect size, respectively. There are insufficient preliminary data

in the literature to support or not support the reasonableness of these effect sizes. For the comparison of serum folate levels among wildtype MTHFR, MTHFR (C677T), and MTHFR (A1298C) patients, ANOVA (unadjusted) and multivariate linear regression will be used.

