#### 4.3.3 Study Summary

Recruitment and Prescreening: see Section 5 descriptions following.

Screening visit (anytime in cycle 1):

1. Obtain informed, signed consent.
2. Complete medical/gynecological/menstrual history and physical exam of female study participant.
  - Vital signs, height, weight, hip and abdominal circumference, BMI
  - Pap smear if necessary per current ACOG time-frame guidelines
  - Standard pelvic and breast exam conducted by physician or within past 12 months
3. Perform radiological exams.
  - Pelvic ultrasound measuring uterine and ovarian characteristics or within past 3 months
4. Laboratory tests: EGCG and metabolites, liver function, folate, estrogen levels, genetics sample collection and urine pregnancy test.
5. Dispense Green Tea extract and educate on dietary restrictions while taking Green Tea extract and with the importance of taking food. All patients to start Green Tea extract at this visit.
6. Contraception education. Patients will be counseled to use non-hormonal double-barrier method: a male/female condom plus spermicidal agents, cervical cap, diaphragm or sponge.
7. Concomitant medication collection.

Visit 1 (Day 1-5):

Patient will be seen on menstrual cycle day  $3 \pm 2$  days for clomiphene citrate/letrozole initiation visit

1. Vital signs and weight.
2. Laboratory tests: EGCG levels over 8 hours (0.5,1,2,4,6,8), liver function, folate, estrogen level, and urine pregnancy testing.
3. Concomitant medication collection and pill counts of EGCG.
4. Randomization and dispensation of clomiphene citrate/letrozole.
5. Contraception education. Patients will be counseled to use non-hormonal double-barrier method: a male/female condom plus spermicidal agents, cervical cap, diaphragm or sponge.

Visit 2 (day 8-10):

Patient will return several days after final clomiphene citrate/letrozole administration

1. Vital signs and weight.
2. Laboratory tests: EGCG levels over 8 hours (0.5,1,2,4,6,8), liver function, folate, estrogen level and urine pregnancy testing.

3. Concomitant medication collection and pill counts of EGCG and clomiphene citrate or letrozole as appropriate.
4. Contraception education. Patients will be counseled to use non-hormonal double-barrier method: a male/female condom plus spermicidal agents, cervical cap, diaphragm or sponge.

Visit 3 (day 14-16):

1. Pelvic ultrasound via a transvaginal probe or transabdominal transducer evaluation of endometrial thickness and ovarian characteristics.

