**Table 1. Screening labs of study women**

LOCAL LABORATORY BLOOD TESTS	CENTRAL LABORATORY BLOOD TESTS
FRIEND PK PRE-FRIEND PROTOCOL V. 2.1 JUNE 29, 2021	

Hormones	Liver	EGCG and metabolites
Estrogen	Total Bilirubin	EGCG
	ALT/AST	EGC
	Alkaline Phosphatase	ECG
		4'-O-methyl-epigallocatechin
		Genetic polymorphisms related to folate metabolism

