### 6.4 Difference in serum folate levels among wildtype MTHFR, MTHFR (C677T), and MTHFR (A1298C) patients. Statistical Analyses

Since the number of patients for this study is minimal and multiple factors are of concern, descriptive statistics will be used, and the study is expected to be under powered to perform any formal statistical inference. The number, mean, standard deviation, median, interquartile range of the level of the pharmacokinetic parameters of EGCG and 2 of the major metabolites at different time points and the difference from screening to Visit 1 or Visit 2 or Visit 4, and the changes in liver function, hormone levels, endometrial thickness and follicular measurements will be presented for the three treatment groups, and then stratified by age group and/or the presence or absence of uterine fibroid. Patients with a detectable EGCG level at the screening visit will be excluded. For comparison, a two-way ANOVA will be used to compare the effects of the three treatments and the presence of fibroids on the above outcome parameters. With a sample size of 36 patients for the three treatment groups, and 18 subjects with uterine fibroids and 18 without uterine fibroids, with an alpha of 0.05, the power of the study would be 0.44 and 0.85 for a medium (0.25) or large (0.4) effect size, respectively. There are insufficient preliminary data in the literature to support or not support the reasonableness of these effect sizes. For the comparison of serum folate levels among wildtype MTHFR, MTHFR (C677T), and MTHFR (A1298C) patients, ANOVA (unadjusted) and multivariate linear regression will be used.

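### Liver changes are compared between arms with no baseline adjustment and no named reference visit, although two liver panels precede clomiphene or letrozole; covariate adjustment would gain precision, by an amount that depends on the reference chosen

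*Combined protocol and SAP*

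**What the plan says.** Section 2.6 lists "Changes in liver function between the 3 groups" as a secondary outcome. Section 2.7 states that "the changes in liver function, estrogen levels, endometrial thickness, and follicular measurements will be presented for the three treatment groups", with further breakdown by age group and fibroid status. For the comparison itself, sections 2.7 and 6.4 specify that "a two-way ANOVA will be used to compare the effects of the three treatments and the presence of fibroids on the above outcome parameters". No baseline liver value is named in that model. Regression is planned only for folate by MTHFR genotype, where "ANOVA (unadjusted) and multivariate linear regression will be used".

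The only reference visit named is in "the difference from screening to Visit 1, Visit 2 or Visit 4", which belongs to the clause on EGCG and metabolite levels. The liver clause that follows names none. The same section warns that "descriptive statistics will be used, and the study is expected to be under powered to perform any formal statistical inference".

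Sections 2.4 and 4.3.3 schedule liver panels at screening and at Visits 1, 2 and 4. In the Visit 1 list of section 4.3.3, the laboratory item includes "liver function, folate, estrogen level, and urine pregnancy testing" and comes before the item for randomisation and dispensing. All women start EGCG at screening. As far as its layout can be read, Table 1 puts bilirubin, ALT/AST and alkaline phosphatase under "LOCAL LABORATORY BLOOD TESTS".

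**The concern.** A change score fixes the coefficient of the baseline value at 1. In a randomised comparison, a model that estimates this coefficient has residual variance no larger than the change score's, and smaller when between-visit correlation is well below 1. A change from one panel also leaves the other pre-assignment panel unused. With 12 women per arm, that loss of precision is worth avoiding if it costs nothing to avoid.

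The liver comparison matters more than its place in the outcome list suggests. Section 4.1 puts hepatic safety beside pharmacokinetics in the only stated aim, and section 5.2 says the results will support hepatic safety for the larger study.

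The missing reference visit is a second gap. Screening precedes EGCG, whereas Visit 1 is on EGCG but precedes the ovulation drugs. Changes from the two visits therefore answer different questions, and the choice could be made after the data are seen.

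**Working it through.** **The plan's own figure.** Sections 2.7 and 6.4 state power of 0.44 and 0.85 at effect sizes f = 0.25 and 0.40 for N = 36, alpha 0.05. With noncentrality N × f² (36 × 0.0625 = 2.25 and 36 × 0.16 = 5.76), 2 numerator and 30 error df, the three-arm test has power 0.23 and 0.52. The stated figures appear at N = 72 (0.443 and 0.853). That discrepancy is a separate matter. It is noted here because the planned ANOVA has less power to spare than the plan suggests.

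**Inputs.** From the documents: 36 women, equal allocation (12 per arm), 18 with and 18 without fibroids, two liver panels before the randomised drug. Not in the documents: the SD and between-visit correlation of the liver tests. Assumed: equal variances (set to 1) and one common correlation ρ, shown from 0.3 to 0.9.

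**Variance of the outcome analysed, one follow-up visit**
- Change from one panel: 2(1−ρ)
- Change from the mean of both panels: 1.5(1−ρ)
- ANCOVA on both panels (or on their mean, which is the same under equal correlation): (1−ρ)(1+2ρ)/(1+ρ)

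The ANCOVA ratio is (1+2ρ)/(2(1+ρ)) against the first and (1+2ρ)/(1.5(1+ρ)) against the second. Estimating two slopes from 30 error df multiplies the ANCOVA variance by about 1 + 2/27 = 1.074.

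| ρ | Ratio to change from one panel | with slope cost | Ratio to change from mean of both | with slope cost |
|---|---|---|---|---|
| 0.3 | 0.615 | 0.661 | 0.821 | 0.881 |
| 0.5 | 0.667 | 0.716 | 0.889 | 0.955 |
| 0.7 | 0.706 | 0.758 | 0.941 | 1.011 |
| 0.9 | 0.737 | 0.791 | 0.982 | 1.055 |

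Against a single panel the saving is 38% to 26%, or 34% to 21% with the slope cost. Against the averaged panels it is 18% to 2%, or 12% down to a small loss. Using the mean of the panels as one covariate costs only 1 + 1/28 = 1.036. The last column is then 0.850, 0.921, 0.975 and 1.018.

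**Where the gain comes from.** Averaging the panels saves 25% of the single-panel variance at any ρ (1.5 against 2). The rest comes from estimating the slopes. Under this model they sum to 2ρ/(1+ρ), which is 0.46, 0.67, 0.82 and 0.95, so the advantage over a fixed coefficient of 1 fades as ρ rises.

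**Power, for illustration.** Three arms of 12, a 1-SD shift in one arm (not a documented effect), fibroid status additive, 3,000 runs per setting:

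| ρ | Change from screening | Change from mean of both | ANCOVA on both |
|---|---|---|---|
| 0.3 | 0.51 | 0.64 | 0.71 |
| 0.5 | 0.67 | 0.78 | 0.81 |
| 0.7 | 0.89 | 0.96 | 0.96 |

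Repeat runs agreed to within 0.02, and type I error of the two methods compared was 0.044-0.055.

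**Unequal correlation.** With correlations of 0.7 (screening–Visit 1), 0.6 (screening–follow-up) and 0.7 (Visit 1–follow-up), the saving before slope cost is 39% against change from screening and 19% against change from Visit 1.

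**The case against.** The strongest reply is that the plan calls itself descriptive and underpowered, ranks liver change as secondary, and promises means, SDs, medians and interquartile ranges with no intervals to narrow. The liver stopping criteria in section 4.3.6 act on individual threshold events, which no model of mean enzymes would change. This limits the importance of the point. It does not remove it, because the same sections specify an ANOVA, an alpha and a power for these outcomes.

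A second reply is that a change from the averaged panels would capture most of the gain. That is correct, as the tables show. But the plan does not say it will average them.

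Third, equal correlation is doubtful: screening is off EGCG and may fall anywhere in the cycle, while Visit 1 is on EGCG after a variable interval. This also stands, and it is why the size is given only as a range.

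In the schedule in section 5.9, as extracted, the randomisation mark appears under Visit 2. This may be an extraction fault, since sections 2.4 and 4.3.3 both place it at Visit 1. Under either reading, the screening and Visit 1 panels precede assignment.

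**Conclusion.** The concern holds as a conditional one. The between-arm liver comparison has no baseline covariate and no defined reference visit, although two pre-assignment panels are available. If the change is taken from a single panel, ANCOVA on both would reduce variance by about 21-34% after slope cost, so standard errors fall by about 11-19%. If the change is taken from the mean of both, the reduction is about 12% at ρ = 0.3, 5% at 0.5, and none at 0.7 or above with two covariates. All of this assumes a common correlation that the documents do not supply.

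Stronger readings are not supported:
- A reader might infer that the plan throws away a third of its precision. That needs a correlation near 0.5, a change from one panel only, and no slope cost. The documents state neither of the first two.
- Dividing 36 by the uncorrected ratios suggests 58, 54 or 51 equivalent women at ρ = 0.3, 0.5 and 0.7. With the slope cost the figures are about 54, 50 and 47, and only against a single panel.
- A reader might take every liver rule to be in multiples of the upper limit of normal (ULN). The exclusion criterion for bilirubin is in mg/dL, and section 4.3.6 also uses INR.
- Four separate local laboratories would be an inference from four sites.

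The change is worth making because it is nearly free, but the outcome is secondary and the study largely descriptive.

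**What to change.** In sections 2.7 and 6.4:

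1. State which panels form the liver baseline, and that the Visit 1 value is the sample taken before clomiphene or letrozole is dispensed.
2. Compare each liver test between arms at Visit 2 and at Visit 4 by ANCOVA, with treatment and fibroid status as factors and the screening and Visit 1 values as covariates. Their mean as a single covariate is a reasonable alternative and saves a degree of freedom.
3. Preferably analyse the log of the value divided by the testing laboratory's ULN, with covariates on the same scale, because liver tests are listed as local. A fixed laboratory factor cancels from a log change, but not from an ANCOVA whose slopes sum to less than 1, so the scaling should be written down.
4. Report adjusted ratios of each combination arm to EGCG alone with 95% intervals.
5. Keep change from screening as the descriptive summary of the EGCG effect, since Visit 1 is already on EGCG and a change from it would miss any early effect.

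The cost is SAP wording and one or two error degrees of freedom, from 30 if the treatment-by-fibroid interaction is fitted or from 32 if it is not. No new data are needed.

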### 2.4 Treatment

The 36 women will be randomized to one of the following groups:

1. EGCG daily alone.
2. EGCG daily with clomiphene citrate 100mg for 5 days.
3. EGCG daily with letrozole 5mg for 5 days.

The purpose of studying EGCG in combination with clomiphene citrate or letrozole is to assess the safety of using them together prior to the initiation of the FRIEND study. It is expected that EGCG will decrease fibroid size and decrease humoral activity leading to improved quality of endometrium for implantation. Clomiphene citrate and letrozole are being used for ovulation stimulation as treatment for unexplained infertility. In view of the possibility of interaction and change in toxicity when both are used together for FRIEND study, it was suggested by our pharmacology reviewer to include EGCG with the addition of clomiphene citrate and letrozole for the safety study.

The initial screening visit will include EGCG levels, liver function, folate and estrogen levels. A genetics sample collection, urine pregnancy test and pelvic ultrasound will also be performed after informed consent. Patient will be given the EGCG (Green Tea extract) to start after the screening visit. Patients will be counseled on dietary restrictions while on EGCG.

Visit 1 will occur on menstrual cycle day  $3 \pm 2$  days. EGCG levels over 8 hours, liver function, and urine pregnancy testing will occur at this visit. Patients will be assigned into their groups and provided with their respective treatments at this visit.

Patient will return between days 8-10 of the cycle for Visit 2. EGCG levels over 8 hours, liver function, estrogen, and urine pregnancy testing will occur at this visit.

The patient will return for Visit 3 between days 14-16 for a pelvic ultrasound evaluation of endometrial thickness and ovarian characteristics.

The final study visit (Visit 4) will be approximately 4 weeks after initiation of the study treatment and will involve EGCG levels, liver function, folate, and urine pregnancy test and pill counts.

The 4 lab panels (screening, Visits 1, 2, and 4) will include EGCG and metabolite analyses, liver panel (AST, ALT, total bilirubin, ALP) and estrogen levels, and a urine pregnancy test. The EGCG analyses at visits 1 and 2 will include testing over 8 hours.

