## 5.7 Transvaginal Ultrasound Exam

An ultrasound exam will be performed with a transvaginal probe. For subjects who cannot tolerate a transvaginal probe, a transabdominal ultrasound evaluation will be performed. The following measures will be obtained at screening: uterine dimensions, leiomyoma presence and size, other uterine abnormalities, endometrial thickness, ovarian size in three dimensions, the size of the largest ovarian follicle, follicle count in the largest plane and ovarian morphology. Ovarian size is determined by measuring the largest plane of the ovary in two dimensions and then turning the vaginal probe 90 degrees and obtaining a third measurement. Endometrial thickness is the largest anterior-posterior measurement of the endometrium in the sagittal plane. Ovarian volume is determined by the formula for a prolate ellipsoid (length x width x height x  $\pi/6$ )(Pache, Hop et al. 1991). If the patient has had no prior test of tubal patency, this may be the desired time to perform a sonohysterogram to determine tubal patency. Only endometrial thickness and ovarian follicular measurements will be measured at visit 2.

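### Follicular measurements have two conflicting visit dates; if cycle day 14-16 stands, the between-arm comparison mixes women who have and have not yet ovulated

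*Combined protocol and SAP*

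**What the plan says.** Section 2.6 lists as a secondary outcome "Changes in endometrial thickness and ovarian characteristics between the 3 groups". Section 2.7 (repeated in 6.4) says that "the changes in liver function, estrogen levels, endometrial thickness, and follicular measurements will be presented for the three treatment groups", and adds: "For comparison, a two-way ANOVA will be used to compare the effects of the three treatments and the presence of fibroids".

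The documents disagree on when the on-treatment measurement is made:

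- Section 2.4: "The patient will return for Visit 3 between days 14-16 for a pelvic ultrasound evaluation of endometrial thickness and ovarian characteristics".
- Section 4.3.3, under Visit 3 (day 14-16): "Pelvic ultrasound via a transvaginal probe or transabdominal transducer evaluation of endometrial thickness and ovarian characteristics". The Visit 2 list in that section has no ultrasound.
- Section 5.7: "Only endometrial thickness and ovarian follicular measurements will be measured at visit 2". Section 2.4 puts Visit 2 at cycle days 8-10.

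Section 5.7 names the follicle measures as "the size of the largest ovarian follicle, follicle count in the largest plane and ovarian morphology", in its list for the screening scan. For the later scan the documents speak only of ovarian characteristics or follicular measurements.

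On the drugs given in arms 2 and 3, Section 2.4 says: "Clomiphene citrate and letrozole are being used for ovulation stimulation". Arm 1 receives EGCG alone. Estrogen is the only hormone in the laboratory lists (4.3.3, and Table 1 in 5.8). LH, progesterone and serial scans are not planned. Nothing says how to score a woman who has already ovulated.

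**The concern.** Largest-follicle size measures growth only until ovulation. Afterwards the dominant follicle is gone and the largest one left is a small residual follicle. With a single scan at day 14-16, a low value can mean that little grew, or that a follicle grew well and has ruptured. A mean over both kinds of women has no clear reading.

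If the share already ovulated were equal across arms, the main cost would be noise and a diluted contrast. Here two arms receive drugs meant to act on ovulation and one does not, so the share may depend on treatment. The pooled comparison could then understate a real difference in follicular response, or show it in the wrong direction. Unless ovulation status is noted at the scan, no other planned measurement can reliably recover it later.

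**Working it through.** **1. The plan's own figure.** The documents give no figure for ovulation day or follicle size. The only figure for this ANOVA is power of 0.44 and 0.85 at effect sizes 0.25 and 0.40. With N = 36, noncentrality f²N is 0.0625 × 36 = 2.25 and 0.16 × 36 = 5.76; the treatment main effect (df 2, 30, alpha 0.05) then has power 0.23 and 0.52. The stated pair does not reproduce at N = 36. That is a separate matter, and nothing below depends on it.

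**2. Which visit.** Sections 2.4 and 4.3.3 agree on Visit 3; one sentence in 5.7 says Visit 2. The columns of the 5.9 schedule are out of line in the text available for this review, so it was not used to settle the question.

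**3. Share already ovulated (assumption).** Take ovulation day as normal with mean μ and SD s, and scans spread evenly over days 14, 15 and 16. Share = average of Φ((day − μ)/s).

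| Mean ovulation day | SD 2 | SD 3 |
|---|---|---|
| 13 | 0.82 | 0.74 |
| 14 | 0.68 | 0.63 |
| 15 | 0.50 | 0.50 |
| 16 | 0.32 | 0.37 |
| 17 | 0.18 | 0.26 |
| 18 | 0.08 | 0.17 |

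The same formula at days 8, 9 and 10 gives 0.03 (SD 2) to 0.10 (SD 3) at mean day 13, and less for later means.

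**4. Effect on the pooled mean (assumption).** Model: size = peak − 2 mm × (ovulation day − scan day), floor 6 mm, if not yet ovulated; 8 mm residual if ovulated; SD of ovulation day 2.5. The later arm peaks at 22 mm and the earlier arm at 24 mm, a true difference of +2 mm.

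Worked case, mean ovulation days 16 (later) and 14 (earlier):

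- Later arm: share ovulated 0.352, mean before ovulation 17.0 mm. Pooled mean = 0.352 × 8 + 0.648 × 17.0 = 13.8 mm.
- Earlier arm: share ovulated 0.648, mean before ovulation 20.5 mm. Pooled mean = 0.648 × 8 + 0.352 × 20.5 = 12.4 mm.
- Earlier minus later = −1.4 mm, against a true +2 mm.

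Other settings, earlier minus later:

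| Mean days (later vs earlier) | Residual follicle | Difference |
|---|---|---|
| 14 vs 12 | 8 mm | −2.0 mm |
| 15 vs 13 | 8 mm | −2.0 mm |
| 17 vs 15 | 8 mm | −0.3 mm |
| 18 vs 16 | 8 mm | +1.2 mm |
| 16 vs 15 | 8 mm | +0.1 mm |
| 17 vs 16 | 8 mm | +0.9 mm |
| 16 vs 14 | 12 mm | −0.3 mm |
| 16 vs 14 | 15 mm | +0.6 mm |

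**5. A second set of assumptions.** Peaks 21 and 23 mm (SD 2.5), growth 1.7 mm/day, residual 7 mm (SD 2), two-day shift, SD of ovulation day 2.5. For a later-arm mean day of 14, 15, 16, 17 and 18 the difference is −2.1, −2.2, −1.8, −0.7 and +0.7 mm. With 36/3 = 12 women per arm, the arm with the larger true peak looks smaller in 83%, 81%, 75%, 61% and 39% of simulated trials.

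**6. Restricting to women not yet ovulated.** Under the model in step 4 with equal 22 mm peaks and mean days 16 vs 14, this subset averages 17.0 and 18.5 mm: a spurious 1.5 mm in favour of the earlier arm. Under the second model, with equal peaks, the spurious gap is 0.7 to 2.0 mm.

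**7. If Visit 2 is meant.** Under the second model at days 8-10, with equal peaks, a two-day shift and a later-arm mean day of 14-16, at most 13% have ovulated. The earlier arm reads 1.5 to 2.2 mm larger, so the reversal does not occur.

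**The case against.** A reader might infer that many women will have ovulated by the scan and that the arm ovulating earlier will look as if it has smaller follicles. The documents do not support that. They give no ovulation day, follicle size, growth rate or residual size, and do not say which arm ovulates earlier. The reversal is fragile: in step 4 it disappears when the shift is one day (16 vs 15), when ovulation is late in both arms (18 vs 16), or when the residual follicle is 15 mm. In the worked case the standard error of the difference at 12 per arm is about 2.3 mm, larger than the −1.4 mm itself.

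A reader might also infer that ovulation will go unrecorded. The ultrasound form is not in the documents, and ovarian characteristics could be taken to include a corpus luteum. The plan's text does not require it, and that is all that can be said. Likewise, largest-follicle size as the on-treatment measure is inferred from the screening list.

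Section 5.7 also counts against the concern: if Visit 2 is the intended visit, the problem largely goes away.

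Finally, Sections 2.7 and 6.4 call the study descriptive and underpowered for formal inference, and no decision rule uses follicle size. That limits the consequence. It does not remove the ambiguity, because means by arm carry the same mixture and the ANOVA is still specified.

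**Conclusion.** The point holds in conditional form. First, Sections 2.4 and 4.3.3 conflict with 5.7 on the visit at which follicular measurements are taken. Second, if Visit 3 stands, the planned comparison combines two opposite meanings of a small value, and nothing in the plan's text separates them.

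The size rests on assumptions outside the documents: 8% to 82% already ovulated for a mean ovulation day of 18 down to 13 (SD 2-3). With SD 2.5, a true +2 mm peak difference reads as about −2.0 to +1.2 mm under the first model and −2.2 to +0.7 mm under the second. So the contrast may shrink and, under some assumptions, reverse; reversal is not the expected result in every setting. One component of a secondary outcome is affected, and the pharmacokinetic primary comparison is not. This is a cheap improvement rather than a threat to the trial's main conclusions.

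**What to change.** 1. Reconcile Sections 2.4 and 4.3.3 with 5.7, and check 5.9, so that one visit is named for endometrial thickness and follicular measurements. Name the on-treatment follicle measures as well.
2. If Visit 3 stands, add one field to its scan form: ovulation has occurred, yes/no (collapsed follicle or corpus luteum seen).
3. In 2.7 and 6.4, make the proportion ovulated by arm the main ovarian summary, and state that the pooled largest-follicle ANOVA will not be interpreted as follicular response.
4. Follicle size in women not yet ovulated may be listed descriptively, with a statement that this subset is selected by ovulation timing and is not a between-arm comparison (step 6 shows why).

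Cost: one form field on a scan already scheduled and a sentence or two in 2.7 and 6.4. No visit or blood draw is added. The downside is a follicle-size table with fewer women per cell.

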#### 4.3.2 Study Population

Thirty-six (36) patients will be equally randomized via computer-generated randomization schedule to receive:

1. Two capsules of decaffeinated Green Tea extract (close to 800mg EGCG) taken orally on a daily basis for up to 2 months
2. Two capsules of decaffeinated Green Tea extract taken orally on a daily basis for up to 2 months with clomiphene citrate 100mg for 5 days
3. Two capsules of decaffeinated Green Tea extract taken orally on a daily basis for up to 2 months with letrozole 5mg for 5 days.

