### 6.2 Primary Outcome Measurements

The primary outcome parameter will be differences in pharmacokinetic parameters of EGCG and 2 of the major metabolites between the 3 treatment groups.

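### The primary outcome ranks no pharmacokinetic parameter, and the one alpha and power statement is tied to no named test; name one primary comparison and restate its power for 36 patients

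*Combined protocol and SAP*

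**What the plan says.** Section 6.2 defines the primary outcome as "differences in pharmacokinetic parameters of EGCG and 2 of the major metabolites between the 3 treatment groups". Section 2.5 is the same in substance but does not limit the metabolites to two. Neither section names a parameter (AUC, Cmax or other), a lead analyte or a visit. Table 1 lists three compounds besides EGCG and does not say which two are meant.

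Sections 2.7 and 6.4 say that descriptive statistics will be used and that "the study is expected to be under powered to perform any formal statistical inference". They list pharmacokinetic parameters at several time points, changes from screening to Visits 1, 2 or 4, and changes in liver function, estrogen (hormones in 6.4), endometrial thickness and follicular measurements. Then "a two-way ANOVA will be used to compare the effects of the three treatments and the presence of fibroids on the above outcome parameters".

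The only significance level is in the power sentence of 2.7: "with an alpha of 0.05, the power of the study would be 0.44 and 0.85 for a medium (0.25) or large (0.4) effect size". It names no outcome and no factor. No hierarchy, multiplicity adjustment or exploratory label is given. Folate by MTHFR genotype has its own ANOVA and regression.

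**The concern.** The same paragraph disclaims formal inference and sets out a hypothesis test with an alpha and a power. With nothing ranked, the headline parameter, analyte and visit can be chosen after the data are seen, and a reader cannot tell which test the 0.05 and the power belong to.

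This matters because of how the results will be read. Section 2.4 explains that the combinations are studied because of a possible interaction, and sections 3.1 and 5.2 say that the results will support the larger FRIEND trial. A nominal difference on one metabolite parameter could be taken as an interaction signal. In the other direction, a power statement that is too favourable could lead someone to take a non-significant result as evidence of no interaction.

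**Working it through.** **Inputs from the documents.** N = 36, with 18 women with and 18 without fibroids (2.7). "Thirty-six (36) patients will be equally randomized via computer-generated randomization schedule to receive" one of three regimens (4.3.2), so 36/3 = 12 per arm and about 12/2 = 6 per arm-by-fibroid cell. Alpha 0.05. Effect sizes 0.25 and 0.40. Stated power 0.44 and 0.85.

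**Assumptions.** The effect sizes are Cohen's f. The layout is a balanced 3 × 2 ANOVA with interaction, so error df = 36 − 6 = 30. The documents do not give the number of tests or the correlations between outcomes, so both are varied.

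**Step 1: the plan's own power figure.** Power = P(F′ > F crit), where F′ is noncentral F with λ = f²N. For the treatment effect (2 and 30 df), F crit = 3.316.

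- f = 0.25: λ = 0.0625 × 36 = 2.25, power 0.229.
- f = 0.40: λ = 0.16 × 36 = 5.76, power 0.521.
- The fibroid effect (1 and 30 df) gives 0.306 and 0.642.

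Neither pair matches 0.44 and 0.85. With N = 72 (2 and 66 df), λ = 4.5 and 11.52, and power is 0.443 and 0.853, which matches both. Seventy-two is 12 per cell × 6 cells, so 12 per arm may have been entered as 12 per cell; the documents do not show this. A repeated-measures set-up with 4 measures and correlation 0.3 also comes close (0.445 and 0.854), but the plan names a two-way ANOVA and gives no correlation or number of measures.

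**Step 2: chance of at least one false treatment difference.** For k independent tests at 0.05 it is 1 − 0.95^k. For correlated outcomes the 3 × 2 ANOVA was simulated with 6 per cell, counting the treatment factor only.

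| Family (assumed) | k | Independent | With correlation |
|---|---|---|---|
| One parameter for each of 3 analytes | 3 | 14.3% | about 10-14% (common r 0.8 to 0.2) |
| AUC and Cmax for 3 analytes | 6 | 26.5% | about 17-23% (within-analyte r 0.8-0.9, between-analyte r 0.2-0.5) |
| Post-randomization outcomes, as listed below | 22 | 67.6% | about 26-62% (common r 0.8 to 0.2) |

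The ranges carry simulation error of a percentage point or so. The 22 are: 6 pharmacokinetic parameters at Visit 2; 3 analyte levels at Visit 4; 4 liver tests and estradiol at two visits (5 × 2 = 10); endometrial thickness; and 2 follicle measures (6 + 3 + 10 + 1 + 2 = 22). Visit 1 pharmacokinetics are left out because section 4.3.3 randomizes and dispenses clomiphene or letrozole at that visit.

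**Step 3: when would a false difference be more likely than not?** 1 − 0.95^13 = 0.487 and 1 − 0.95^14 = 0.512, so 14 independent tests are needed. A primary family of 3 or 6 is well short of that.

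**The case against.** The strongest reply is that the plan calls itself descriptive and never offers 0.05 as a trial-wide error rate. That stands. A reader might infer that any single p<0.05 would meet the primary outcome, but sections 2.5 and 6.2 say only what is compared; they give no hypothesis, threshold or success rule. Nor does any section let a pharmacokinetic p-value decide about the next trial, and the termination rule in 4.3.6 rests on liver cases, not on ANOVA.

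Three other tempting readings also go too far:

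- That every outcome goes through the two-way ANOVA. Folate has a separate analysis, and change in pharmacokinetics within a group is not a between-group question.
- That the fibroid tests add to the primary error rate. The primary outcome is a comparison between the treatment groups only.
- That a false primary difference is likely. At 3 to 6 tests it is well above 5% but far below one half.

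It can also be said that deleting the disclaimer would leave a plainly confirmatory test with power of only 0.23 or 0.52. That is right, and the disclaimer should stay in limited form. What the reply does not answer is that the primary parameter is unnamed, and that the alpha and power attach to no test and do not fit 36 patients.

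**Conclusion.** The point holds as one of specification and interpretation. The primary outcome is an unranked family, and the descriptive statement sits unreconciled beside an ANOVA with an alpha and a power. Read at 0.05 per test, the chance of at least one false treatment difference is about two to five times the nominal 5% within the primary family (10-14% for 3 tests, 17-23% for 6), and 26-62% over the assumed 22 outcomes. These figures rest on assumed test counts and correlations. They measure the risk of over-reading a nominal result; they do not show a breach of an error rate that the plan claims.

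The power finding depends less on assumption. With f read as Cohen's f and the ANOVA as planned, 36 patients give 0.23 and 0.52 for treatment, and the stated figures fit 72. The change is worth making and needs only wording.

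**What to change.** In sections 2.5, 2.7, 6.2 and 6.4:

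- Name the treatment effect on EGCG AUC over the 8-hour sampling period at Visit 2, which section 4.3.3 places after the clomiphene or letrozole course, as the single primary comparison at alpha 0.05.
- State how the time-zero value is handled, since the samples listed in 4.3.3 start at 0.5 h.
- Tie the power statement to that test and restate it for N = 36: about 0.23 for f = 0.25 and 0.52 for f = 0.40.
- Report the other two-way ANOVA outcomes, and the fibroid factor, as exploratory estimates with 95% confidence intervals.
- Keep the disclaimer of formal inference, limited to those exploratory outcomes. Say plainly that the primary test has low power, so a non-significant result does not show absence of interaction.

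The cost is protocol and SAP wording. The downside is that a difference on any other parameter, real or chance, can only be called exploratory, and the stated power becomes less favourable.
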